##### **Study Endpoints and Indicator System**

Study endpoints are divided into primary outcome indicators and secondary outcome indicators.

##### **Primary Outcome Indicators**

1. Disease diagnosis task: Area Under the Curve (AUC), Sensitivity, Specificity, Accuracy, F1-score;
2. Lesion localization and segmentation task: Dice coefficient, Hausdorff distance;
3. Report generation task: BLEU, ROUGE, CIDEr, etc.

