## **(III) Patient Inclusion, Exclusion, and Withdrawal Criteria**

### **Inclusion Criteria**

1. Adult patients aged  $\geq 18$  years;
2. Undergoing imaging examinations (CT, MRI, ultrasound, etc.) in the hospital during the study period;
3. Examination items corresponding to the disease types or systems focused on by the study (hepatobiliary and pancreatic system);
4. Possessing at least complete imaging data and radiology diagnostic reports, with relevant medical record information as supplementary modalities;
5. Patients or their legal representatives signing an informed consent form, agreeing to the use of their de-identified data for scientific research model validation;
6. Case data passing quality review, with good imaging quality and standardized text records.

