#### **(IV) Detailed Research Protocol**

##### **Research Data Sources**

Data for this study are derived from patients undergoing routine clinical examinations in the hospital during the study period. Data collection is accomplished relying on the hospital's existing information systems, without imposing additional burdens on patients or interfering with diagnosis and treatment processes. All data are real-world multimodal information generated in routine clinical practice, mainly including:

- Medical imaging data from the Department of Radiology, covering original images and reconstructed sequences such as CT, MRI, and ultrasound, as well as manual annotations, masks, or structured descriptions, which serve as reference standards for model validation;
- Radiology diagnostic reports, including examination findings, diagnostic conclusions, and physician recommendations. All images undergo unified format conversion (e.g., DICOM to NIfTI) and quality assessment before being imported into the study database, with sequences containing artifacts or defects excluded;
- Text data from the electronic medical record system, including admission records, discharge summaries, progress notes, and surgical records. Prior to import, text data undergo automated de-identification to remove sensitive information such as names, hospital admission numbers, ID card numbers, and contact information, retaining only key clinical course points relevant to the research objectives;
- Structured laboratory data from the laboratory information system, including quantitative data such as complete blood count, biochemical indicators, tumor markers, and coagulation function, which are aligned with imaging examinations via timestamps to support cross-modal feature fusion and quantitative analysis of disease states in the model.

All research data undergo rigorous de-identification before being imported into the analysis environment, with only the minimum necessary information required for the study retained. Data collection and usage comply with the Personal Information Protection Law, Data Security Law, and the hospital's ethical requirements. All patients sign a written informed consent form prior to enrollment, explicitly agreeing to the use of their de-identified data for scientific research model validation and performance optimization. The entire research process is conducted under the approval and supervision of the IRB.

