#### **Statistical Analysis Procedures**

This study adopts intention-to-treat (ITT) analysis as the primary analytical strategy, conducting systematic statistical analysis on data from all enrolled cases. First, descriptive statistics are performed to summarize the baseline characteristics of patients, including age, gender, disease type, and imaging equipment source. Continuous variables are presented as mean  $\pm$  standard deviation or median depending on their distribution type, while categorical variables are expressed as frequencies. Inter-group differences are analyzed using appropriate statistical methods based on data characteristics: the t-test is used for normally distributed data, and the Mann–Whitney U test is used for non-normally distributed data.

In the analysis of primary outcome indicators, this study focuses on evaluating the model's performance in three core tasks: disease diagnosis, lesion localization, and report generation. For the disease diagnosis task, clinical final diagnosis or pathological results are used as the gold standard to calculate AUC, Sensitivity, Specificity, Accuracy, and F1-score, and receiver operating characteristic (ROC) curves are plotted to comprehensively assess the model's classification ability. For the lesion localization and segmentation task, expert annotations are used as references to calculate the Dice coefficient and Hausdorff distance, measuring the model's performance in lesion recognition range and boundary precision. For the report generation task, model-generated reports are compared with radiologists' reports at the text level, and natural language generation metrics such as BLEU, ROUGE, and CIDEr are used to evaluate language quality and semantic consistency.

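### Lesion localization is a primary task, yet no indicator counts lesions found, missed or falsely marked, and Hausdorff distance has no finite value for a complete miss or a false mark in a lesion-free patient

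*Protocol*

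**What the plan says.** The Protocol's Statistical Analysis Procedures name "three core tasks: disease diagnosis, lesion localization, and report generation" as the focus of the primary analysis. Under Primary Outcome Indicators, the second task reads "Lesion localization and segmentation task: Dice coefficient, Hausdorff distance", with nothing further. The analysis section adds that "expert annotations are used as references to calculate the Dice coefficient and Hausdorff distance", and gives their purpose as "measuring the model's performance in lesion recognition range and boundary precision".

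Sensitivity and specificity are listed only for the diagnosis task, against the final clinical or pathological diagnosis. The secondary indicators cover agreement on key report conclusions, generalization, efficiency and expert ratings. None is a lesion-level detection measure.

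The primary strategy is described as "conducting systematic statistical analysis on data from all enrolled cases". Entry is by examination: "Undergoing imaging examinations (CT, MRI, ultrasound, etc.) in the hospital during the study period" and "Examination items corresponding to the disease types or systems focused on by the study (hepatobiliary and pancreatic system". No criterion requires a lesion. The study design section, however, describes the enrolled patients as newly diagnosed.

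**The concern.** Localization asks two questions: was each lesion found where it is, and was anything marked that is not a lesion? Dice and Hausdorff answer a different one: how closely do two drawn regions agree? A model can reach the right patient-level diagnosis while missing a second lesion or marking the wrong site, and no listed indicator would count that as a detection error.

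Hausdorff adds a second difficulty. It needs two non-empty masks. If it is averaged wherever it can be computed, it covers only patients in whom the model drew something and a lesion was present. The complete failures are then absent from one of the two primary localization measures, and the reported boundary distance looks better than the model is.

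**Working it through.** The protocol states no target, standard deviation or sample size for this task, so there is no figure of its own to reproduce. The check is of the definitions and then of the possible size.

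**Definitions.** For reference mask A and model mask B:
- Dice = 2|A∩B| / (|A| + |B|).
- Hausdorff = the larger of the two directed maximum distances, from A to B and from B to A. It needs points in both masks.

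**Behaviour on constructed 3-D masks** (spheres in a cube of 120 voxels per side):

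| Situation | Dice | Hausdorff (voxels) |
|---|---|---|
| Only lesion missed | 0 | no finite value |
| False lesion in a lesion-free patient | 0 | no finite value |
| Lesion-free, model correctly empty | 0/0 | no value |
| Lesion marked in the wrong place | 0 | 130 |
| One lesion, radius 20, contour shifted by 3 | 0.888 | 3 |
| The same, with a second lesion of radius 5 missed | 0.881 | 79 |
| Two lesions, radius 20 perfect, radius 5 missed | 0.992 | 80 |

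The last row can be checked by hand. Volumes go with the cube of the radius, so Dice ≈ 2 × 8000 / (8000 + 8125) = 0.992. In that patient half the lesions were missed. Hausdorff does react, but both formulas are symmetric in A and B. A false mark of radius 5 beside a perfectly drawn lesion of radius 20 would give the same pair of values. The pair therefore shows that something is wrong, but neither what nor how often.

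**How many patients could lack a Hausdorff value.** Let N = 2000 (Sample Size Estimation Process), p = share of patients with a lesion, m = share of those missed completely, f = share of lesion-free patients with a false mark. Here p, m and f are assumptions: p = 50–100%, m = 5–30%, f = 10%.
- Patients without a value = N(1 − p) + N·p·m.
- Of these, actual errors = N·p·m + N(1 − p)·f.

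| p | Without a value, m = 5% to 30% | Of which errors |
|---|---|---|
| 100% | 0 + 100 = 100 to 0 + 600 = 600 | 100 to 600 |
| 80% | 400 + 80 = 480 to 400 + 480 = 880 | 80 + 40 = 120 to 480 + 40 = 520 |
| 50% | 1000 + 50 = 1050 to 1000 + 300 = 1300 | 50 + 100 = 150 to 300 + 100 = 400 |

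The first row shows that the gap does not depend on lesion-free patients being enrolled, because complete misses alone produce it.

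**The case against.** The strongest reply is that Dice already penalises the gross errors. That is correct. A complete miss and a false mark in a lesion-free patient each score 0, the worst possible value. Dice lacks a value only for a correctly empty case, which is not an error. The two measures are also paired: Hausdorff exposes the small missed lesion that Dice hides, and a wrong location gives Dice 0 and a large distance.

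Three stronger readings are tempting, and the protocol does not support them.
- A reader might infer that missed lesions drop out of Dice as well, so that the study would report, say, 0.85 (found lesions only) instead of 0.8 × 0.85 = 0.68 with 20% missed. No section limits Dice to detected lesions, and the stated strategy is to analyse all enrolled cases, so this inflation does not follow from the plan.
- A reader might infer that false marks in lesion-free patients go uncounted altogether. Dice counts them if those cases are kept.
- A reader might infer from Research Data Sources, which lists "manual annotations, masks, or structured descriptions, which serve as reference standards for model validation", that Dice is to be computed from structured descriptions. That list covers reference material for validation in general. The analysis section names expert annotations as the reference for this task.

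It is also fair that an empty-mask rule, the unit of scoring and the details of a hit rule may stand in a statistical analysis plan that is not shown. Silence on these is not held against the protocol. The choice of primary measures is different: the protocol makes it, and neither its primary nor its secondary list includes a detection measure.

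**Conclusion.** The point holds in a limited form. A primary task that includes localization has no measure of lesions found or of false lesions marked. Hausdorff, one of its two measures, cannot take a finite value for complete misses or for false marks in lesion-free patients unless a further rule is set. Dice does register those errors if all cases are kept. Its own limits are the undefined correctly empty case and its insensitivity to small missed lesions when masks are pooled.

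The size is uncertain. The lesion-free share is unknown, since entry by examination and the description of patients as newly diagnosed point in different directions, and no miss rate is given. Over the assumed ranges, between 100 and 1300 of 2000 patients would have no Hausdorff value. The absence of a detection measure rests on no assumption. This is an inexpensive improvement to the measure set and does not show that the planned Dice result would be biased.

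**What to change.** In Primary Outcome Indicators and Statistical Analysis Procedures:
- Add lesion-level sensitivity, with a stated hit rule (for example a minimum overlap, or the marked centre lying inside the reference lesion).
- Add false-positive lesions per patient, over all patients including those without a lesion. Every patient then contributes to at least one detection measure.
- Keep Dice, score complete misses and false marks as 0, and report correctly empty cases separately as a count.
- Report Hausdorff as a boundary measure in detected lesions, always next to the number of misses and false marks.

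The cost is protocol wording and some extra analysis of the same model outputs and expert annotations. No new patients or procedures are needed.

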##### **Secondary Outcome Indicators**

1. Clinical consistency: Consistency between model-generated reports and physicians' final reports in terms of key conclusions;
2. Generalization ability: Stability of the model across different devices, disease types,

and populations;

3. Clinical efficiency indicators: Average model inference time, report generation speed, percentage reduction in physician review time;

4. Expert subjective ratings: Scale-based evaluation of the readability and clinical value of model-generated reports by physicians.

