#### **Sample Size Estimation Process**

The sample size for the prospective validation of this study is determined based on statistical power analysis. Assuming the model achieves an accuracy of approximately 85% in the disease diagnosis task, compared with an 80% accuracy rate of manual diagnosis, with an expected detectable performance difference of 5%, a significance level ( $\alpha$ ) set at 0.05, and a test power ( $\beta$ ) set at 0.2, approximately 500–600 cases per group are required according to the binomial distribution sample size calculation formula, with a total of 1000–2000 newly enrolled cases needed to meet statistical significance requirements.

Considering potential loss to follow-up or data disqualification during the prospective study, the final plan is to collect complete multimodal data (including imaging, reports, and laboratory results) from approximately 2000 patients for model validation and performance analysis. This sample size ensures the accurate evaluation of the model's stability, generalization ability, and consistency with expert diagnosis in real-world clinical scenarios at a 95% confidence level.

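### Ten unranked, open-ended metrics are primary, yet the model-versus-manual accuracy difference that sizes the study is neither an endpoint nor an analysis, and the report metrics are credited with measuring meaning

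*Protocol*

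**What the plan says.** Section 3 (IV), Primary Outcome Indicators, has three entries: "Disease diagnosis task: Area Under the Curve (AUC), Sensitivity, Specificity, Accuracy, F1-score"; "Lesion localization and segmentation task: Dice coefficient, Hausdorff distance"; and "Report generation task: BLEU, ROUGE, CIDEr, etc". No entry or metric is ranked above another. Statistical Analysis Procedures introduces the text metrics with 'such as', so it does not close the list.

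The sample size text, in section 3 (IV) and again in section 4, Prospective Study Phase, starts from a comparison: "Assuming the model achieves an accuracy of approximately 85% in the disease diagnosis task", "compared with an 80% accuracy rate of manual diagnosis". It sets a 5% difference, alpha 0.05 and beta 0.2, states 500–600 cases per group, and plans about 2000 patients.

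Statistical Analysis Procedures calculates the five diagnostic metrics for the model against the clinical final diagnosis or pathology. For reports it says that "BLEU, ROUGE, and CIDEr are used to evaluate language quality and semantic consistency". The content-based measure of reports is listed under Secondary Outcome Indicators: "Consistency between model-generated reports and physicians' final reports in terms of key conclusions". It is to be assessed by double-blind physician ratings and Cohen's kappa.

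**The concern.** A primary outcome should identify the question the study answers and match the quantity that sets its size. Here the two separate. The sizing asks whether the model is more accurate than manual diagnosis; the endpoint list describes the model alone. An analyst who follows the endpoint and analysis sections to the letter reports the model's accuracy and never estimates the difference.

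The unranked list ending in 'etc.' adds a second problem. A reader of the final report could not check which result was meant to lead, or whether a metric shown as primary had been planned as one. That invites selective emphasis.

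The third problem is interpretation. If word-overlap scores are presented as evidence of semantic consistency, a report with a wrong key finding can be counted as a good one on a primary outcome.

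**Working it through.** **1. Count of primary metrics.** Diagnosis 5 (AUC, sensitivity, specificity, accuracy, F1-score), segmentation 2 (Dice, Hausdorff), reports 3 (BLEU, ROUGE, CIDEr): 5 + 2 + 3 = 10, plus whatever 'etc.' covers.

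**2. Where the sized comparison appears.**

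| Place in the protocol | Model versus manual accuracy? |
|---|---|
| 3 (I), Study Design Type and Methodology | General statement that results will be compared with clinicians' conclusions; no endpoint attached |
| 3 (IV), Primary Outcome Indicators | Accuracy of the model only |
| 3 (IV), Secondary Outcome Indicators | Not listed |
| 3 (IV), Sample Size Estimation Process; section 4 | Yes: 85% versus 80% |
| 3 (IV), Statistical Analysis Procedures | Model metrics against the gold standard; no manual comparator for accuracy |

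**3. The plan's own sample size.** With independent groups, p1 = 0.85, p2 = 0.80, pooled p = 0.825, power 0.80:

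n per group = [z_α √(2 × 0.825 × 0.175) + 0.842 √(0.85 × 0.15 + 0.80 × 0.20)]² / 0.05²

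- Two-sided: (1.960 × 0.5374 + 0.842 × 0.5362)² / 0.0025 = 906.
- One-sided: (1.645 × 0.5374 + 0.842 × 0.5362)² / 0.0025 = 714.

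The stated 500–600 per group is not reproduced; at that size two-sided power is 0.55 to 0.63. This is a separate matter. What counts here is that the formula is for two independent groups, while the design is one consecutive cohort in which the model and the manual reading concern the same patients.

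**4. The same comparison as paired data.** Let ψ be the proportion of patients in whom exactly one of model and manual diagnosis is correct, and d = 0.05. The protocol gives no ψ, so it is an assumption. For the two-sided McNemar test at alpha 0.05:

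N = [1.960 √ψ + 0.842 √(ψ − d²)]² / d²

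Power at N = Φ{[d√N − 1.960 √ψ] / √(ψ − d²)}

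| ψ (assumed) | N for 80% power | Power with 2000 patients |
|---|---|---|
| 0.10 | 312 | >0.999 |
| 0.15 | 469 | >0.999 |
| 0.20 | 626 | 0.999 |
| 0.25 | 783 | 0.994 |
| 0.29 | 909 | 0.986 |
| 0.35 | 1097 | 0.966 |

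The value 0.29 corresponds to independent errors: 0.85 × 0.20 + 0.15 × 0.80 = 0.29. At ψ = 0.35: (0.05 × 44.72 − 1.960 × 0.5916) / √0.3475 = 1.826, and Φ(1.826) = 0.966.

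**5. What BLEU registers.** Take a 51-token reference report with no repeated n-grams and change one token away from the ends, for example 'No' to 'A' before 'focal lesion'. One of 51 single words, two of 50 pairs, three of 49 triples and four of 48 quadruples no longer match. Length is unchanged, so there is no brevity penalty:

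BLEU-4 = (50/51 × 48/50 × 46/49 × 44/48)^(1/4) = 0.8099^(1/4) = 0.949

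The result is the same whichever mid-text token is changed, so a reversed finding costs no more than a trivial word swap. The calculation is for BLEU. ROUGE and CIDEr also score overlap with a reference text, but were not computed.

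**The case against.** These metrics are conventional in validating diagnostic models, and this is a non-interventional study that calculates them without any success rule. That is right, and it limits the point. A reader might infer that ten primary metrics inflate the family-wise error rate, or that success could be declared on any one of them. The protocol supports neither reading: it states no hypothesis, null value or threshold for most of them, and handling of multiplicity could sit in a statistical analysis plan that is not shown. What remains is an unranked, open list, which the protocol itself fixes.

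Accuracy is on the primary list, and the design section mentions comparison with clinicians. Both are true, but neither makes the difference an endpoint or gives it an analysis.

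A reader might also infer that the clinical content of reports goes unexamined. It does not: kappa on key conclusions and Likert ratings of clinical value are planned, and the design section compares model outputs with the confirmed result. The fault is in the ranking and in the phrase about semantic consistency. Nor is key-conclusion agreement a measure of correctness, because its reference is the physicians' final report and not the gold standard.

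Finally, a reader might conclude that segmentation and report generation should cease to be primary tasks. The protocol names three core tasks, so one lead metric for each fits its objectives; removing whole tasks would be a preference.

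**Conclusion.** The point holds on the text. Ten named metrics plus 'etc.' are primary without rank, the comparison that sizes the study is missing from both endpoints and analysis, and semantic consistency overstates what word-overlap metrics measure. This should be corrected before enrolment starts; it does not prevent the study from running.

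The planned size is ample for the missing comparison: power is at least about 0.97 if ψ lies between 0.10 and 0.35, the true difference is 5 points, and about 2000 patients have a model output, a scored manual diagnosis and a reference diagnosis. The protocol's own figure cannot be carried over unchanged, because it was derived for independent groups.

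One limit applies to the comparison itself. The gold standard may be the clinical final diagnosis, which may incorporate the manual reading. Where it does, manual accuracy is partly scored against itself.

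**What to change.** 1. In Primary Outcome Indicators and Statistical Analysis Procedures, name the within-patient difference in diagnostic accuracy, model minus manual, as the lead primary outcome. Analyse it as paired data, with McNemar's test and a 95% confidence interval for the paired difference. Restate both sample size texts for a paired comparison with an explicit discordance assumption.
2. Delete 'etc.', name one lead metric for each remaining task, and report the other metrics descriptively with 95% confidence intervals.
3. For report generation, lead with the planned key-conclusion agreement, and say that it measures agreement with physicians' final reports. Keep BLEU, ROUGE and CIDEr as descriptive measures of text similarity and remove the claim of semantic consistency.
4. Add a sensitivity analysis of the accuracy difference restricted to pathology-confirmed cases. Their number is not given, so its precision cannot be stated now.

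Cost: no new patient procedures, since model outputs, radiology conclusions and reference diagnoses are already part of the plan. The manual diagnosis must, however, be extracted from routine reports and scored by a defined rule, and some segmentation and report metrics lose primary status.
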